**The current status and progression of
symptoms and comorbidities among
male lower urinary tract symptoms
patients in China: a multicenter study
from Prostatic Obstruction
Investigation Team (POInT)**

December 19, 2017

Title

The current status and progression of symptoms and comorbidities among male lower urinary tract symptoms patients in China: a multicenter study from Prostatic Obstruction Investigation Team (POInT).

Aims

Aim one: To investigate the symptom features and comorbidities among male lower urinary tract symptoms patients in China.

Aim two: To determine the progression of lower urinary tract symptoms and comorbidities after medication or surgical treatment during prospective follow-ups.

Inclusion Criteria

[figure not shown]
1. Male, 45 years or older.
2. The presence of lower urinary tract symptoms, i.e. frequency, urgency, urge incontinence, dysuria, post-micturition dribble, etc.
3. All participants have signed the informed consent form.
4. Clinical data comes from 23 selected hospitals spread across China.

Exclusion Criteria

[figure not shown]
1. Lower urinary tract symptoms as a result of urethral stricture, stone diseases, chronic prostatitis, space-occupying lesions etc.
2. Diagnosis or suspicion of renal, ureteral, bladder, prostate, urethral or pelvic tumor.
3. Known neurogenic or congenital lower urinary tract dysfunction.
4. Known urinary tract, prostate or pelvic surgical history.
5. Existence of anatomical abnormalities of the urinary tract (e.g. diverticulum of the bladder or urethra, ectopic ureteral orifice etc.).
6. The presence of acute conditions, such as, urinary tract infection, fever, heart failure etc.
7. Patients with poor compliance or cognitive competence.

Study design flow diagram

[figure not shown]
Overall design

Stage I

Stage II

Statistical Analysis

The statistical analysis will be performed using sas software version 9.4 or higher. Quantitative data will be presented as mean \pm standard deviation; Categorical and ranked data will be presented using frequency and proportion. Normal distributed and equal variance quantitative data will be analyzed using independent sample t test, otherwise using a Wilcoxon rank sum test. Categorical data will be assessed by Chi-square test and Fisher's exact test. Ranked data will be analyzed by Wilcoxon rank sum test. Multivariate analysis logistic regression will be used to screen risk factors in the binary variables. The level of significance will be established at <0.05 .

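### Aim two is given only unadjusted two-sample tests for quantitative and ranked outcomes: they do not measure within-patient progression, and they cannot separate a treatment effect from baseline differences if medication and surgery are compared

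*Combined protocol and SAP*

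**What the plan says.** The Aims section states Aim two as "To determine the progression of lower urinary tract symptoms and comorbidities after medication or surgical treatment during prospective follow-ups". Medication and surgery are the only patient groupings that the aims mention. The readable text gives no randomisation and no rule for assigning treatment. The flow diagram is not shown, and no text is readable under the Overall design, Stage I and Stage II headings.

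The Statistical Analysis section is one paragraph. It treats outcomes by type:

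- Quantitative: "Normal distributed and equal variance quantitative data will be analyzed using independent sample t test, otherwise using a Wilcoxon rank sum test".
- Ranked: "Ranked data will be analyzed by Wilcoxon rank sum test".
- Categorical: "Categorical data will be assessed by Chi-square test and Fisher's exact test".
- Multivariable: "Multivariate analysis logistic regression will be used to screen risk factors in the binary variables".
- Significance: "The level of significance will be established at <0.05"; sidedness is not stated.

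The paragraph does not name the groups to be compared. It also does not say whether the tested quantity is the follow-up value or the change from baseline. It contains no paired or repeated-measures method and no adjusted method for a quantitative or ranked outcome. The inclusion criteria add that "Clinical data comes from 23 selected hospitals spread across China", but the analysis does not mention centre.

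**The concern.** Two problems follow if the paragraph is applied to Aim two as written.

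First, progression is a change within a patient over time. A test for two independent samples compares two separate sets of men. It does not estimate how far the men in one treatment group moved, and if it is applied to baseline and follow-up values of the same men it ignores the pairing.

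Second, if the two samples are the medication and surgery groups, nothing in the analysis accounts for the groups starting at different points. Without randomisation such differences are to be expected. An unadjusted difference would combine any treatment effect with the effect of who received which treatment, and the test cannot separate them. The apparent direction can depend on whether the follow-up level or the change is tested, and the plan leaves that open. A reader of the results could be told that one treatment does better when the two are equal.

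**Working it through.** The plan states no sample size, effect size, SD, group sizes or follow-up length, so there is no figure to reproduce. Everything below is illustrative. From the documents: significance level 0.05 (two-sided assumed), independent two-sample tests, 23 hospitals. Assumed: d (baseline gap, surgery minus medication, in SD; a higher score is worse), r (baseline/follow-up correlation), n per group, and equal benefit of both treatments.

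**1. Ignoring the pairing.** For n men with unit SD, the variance of the mean change is 2(1−r)/n, while an independent-sample test uses 2/n. The standard error is too large by 1/√(1−r): 1.20 at r = 0.3, 1.41 at r = 0.5 and 1.83 at r = 0.7.

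**2. Bias in a medication-versus-surgery contrast, selection on the observed baseline score.** The follow-up gap is r·d, so:

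- bias in follow-up level = r·d (surgery looks worse);
- bias in change = r·d − d = −(1−r)·d (surgery looks better).

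At d = 0.5 and r = 0.5 these are +0.25 and −0.25 SD.

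**3. False-positive rate.** The test statistic has mean z = bias/(s·√(2/n)), with s = 1 for the level and s = √(2(1−r)) for the change. The rejection rate is 1 − Φ(1.96 − z) + Φ(−1.96 − z). For d = 0.5, r = 0.5, n = 100: |z| = 0.25/√0.02 = 1.77 for both, which gives 0.424. A simulation of 4000 studies gave 0.420 (level), 0.426 (change) and 0.049 after adjustment for baseline.

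Ranges over r = 0.3 to 0.7:

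| d (SD) | n = 100, level | n = 100, change | n = 300, level | n = 300, change |
|---|---|---|---|---|
| 0.2 | 0.071–0.168 | 0.085–0.133 | 0.114–0.403 | 0.158–0.305 |
| 0.5 | 0.186–0.697 | 0.278–0.552 | 0.451–0.990 | 0.660–0.952 |
| 0.8 | 0.396–0.977 | 0.591–0.917 | 0.836–1.000 | 0.967–1.000 |

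**4. A different selection mechanism.** Suppose instead that surgery depends on underlying severity, and that baseline and follow-up scores are both noisy measures of it. With equal benefit the gap is d at both times (r is now the within-group correlation):

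- follow-up level: bias d;
- change: bias d − d = 0;
- baseline-adjusted: bias d − r·d = (1−r)·d.

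At d = 0.5, r = 0.5, n = 100:

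- Level: z = 0.5/√0.02 = 3.54, rejection 0.94.
- Change: rejection 0.05.
- Adjusted: standard error = √((1−r²)·(2/n)·(1+d²/4)) = √(0.75 × 0.02 × 1.0625) = 0.126, z = 0.25/0.126 = 1.98, rejection about 0.5.

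**5. Larger gaps.** Assumed: 300 men, 90 with surgery and 210 with medication, gap about 0.7–1.3 SD, r = 0.5–0.8, 1000 samples per setting.

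| Selection acts on | Unadjusted change | Baseline-adjusted |
|---|---|---|
| observed baseline score | 37–100% | 4–7% |
| underlying severity | 4–6% | 44–100% |

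Under selection on the observed score, the unadjusted follow-up-level test rejects in 74–100%.

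**The case against.** The strongest reply is that the criticised comparison is not in the plan. Aim two is worded descriptively, the tests have no named grouping variable, and they could serve subgroup comparisons under Aim one. This stands: the confounding argument is conditional on medication and surgery being compared. It does not rescue the descriptive reading, because the paragraph contains no method for within-patient change either.

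A reader might infer that treatment is chosen by clinical need. The documents do not say so. The readable text describes no allocation, but the flow diagram and stage text are not available, so one can say only that no randomisation is described.

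A reader might also infer that an unadjusted difference would show nothing but selection for surgery. That is too strong: it would mix selection with any real treatment effect.

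Finally, the favourable result for baseline adjustment in step 3 comes from making the observed baseline score the only confounder. Step 4 shows that under selection on underlying severity the change-score test holds its level and the adjusted test does not. This also stands. Adjustment improves on the unadjusted follow-up-level test under both mechanisms, but it is not a guarantee of 5%, and it can do worse than the unadjusted change test.

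**Conclusion.** The concern holds in a conditional form. For quantitative and ranked outcomes, the Statistical Analysis section gives Aim two neither a within-patient analysis nor any control for baseline differences. This is a stated method that does not fit the aim, which is more than missing detail. The logistic model does not fill the gap, since it is confined to binary variables.

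If the treatments are compared, the false-positive rate depends on the baseline gap, the correlation, the sample size and how men come to each treatment. Under selection on the observed score with 100 men per group it runs from 7–17% at a 0.2 SD gap to 40–98% at 0.8 SD. Under selection on underlying severity, the follow-up level remains biased and the change does not. All these inputs are assumed. The qualitative conclusion, that the tests cannot separate treatment from baseline differences, needs only that the groups may differ at baseline. The point should be addressed; confidence is medium because part of the design description cannot be read.

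**What to change.** Amend the Statistical Analysis section as follows.

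1. State that the primary Aim two result is progression within each treatment group, analysed as within-patient change.
2. For any medication-versus-surgery contrast in a quantitative outcome, replace the unadjusted test by a linear regression of the follow-up value on treatment, adjusted for the baseline value of the same measure, age, baseline comorbidities and centre. Use an ordinal regression for ranked data.
3. Show the covariate-adjusted change-score result beside it as a sensitivity analysis. The two models rest on different assumptions about selection, and a disagreement between them should be reported.
4. Describe the contrast as an association, not a treatment effect.

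The cost is about a paragraph of SAP wording and slightly more analysis. No new data are needed if baseline symptoms and comorbidities are collected for Aim one. The downside is a weaker claim: confounding by unmeasured or imprecisely measured severity remains, and adjustment for the observed baseline does not guarantee the nominal 5% error rate.

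### The analysis text takes no account of patients being grouped in 23 hospitals, so p-values can be too small when a factor and the outcome both vary by hospital

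*Combined protocol and SAP*

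**What the plan says.** The title calls this "a multicenter study", and item 4 of the Inclusion Criteria reads "Clinical data comes from 23 selected hospitals spread across China".

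The Statistical Analysis section sets a test for each type of data:

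- Quantitative: "Normal distributed and equal variance quantitative data will be analyzed using independent sample t test, otherwise using a Wilcoxon rank sum test".
- Categorical: "Categorical data will be assessed by Chi-square test and Fisher's exact test".
- Ranked: "Ranked data will be analyzed by Wilcoxon rank sum test".
- Risk factors: "Multivariate analysis logistic regression will be used to screen risk factors in the binary variables".
- Threshold: "The level of significance will be established at <0.05".

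It mentions no hospital or centre term, stratification, random effect, GEE or cluster-robust variance. The flow diagram is not shown, and the Overall design, Stage I and Stage II headings carry no readable text. The point therefore concerns the readable analysis text only.

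**The concern.** In their standard form, all the named methods assume that patients are independent. Patients at one hospital tend to resemble each other through case mix, referral, treatment habits and measurement practice. If a factor also clusters by hospital, the ordinary standard error is too small and the p-value with it.

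This matters most for the risk-factor model, where the 0.05 threshold appears to decide which factors are reported. Adjusting for other patient characteristics does not remove hospital differences.

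A second, conditional issue concerns Aim two: "To determine the progression of lower urinary tract symptoms and comorbidities after medication or surgical treatment during prospective follow-ups". The analysis section does not say that medication and surgery will be compared. If they are, and hospitals differ both in how often they operate and in how their patients fare, hospital would also confound the estimate, not merely distort its p-value.

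**Working it through.** **Inputs from the documents.** 23 hospitals (Inclusion Criteria, item 4) and a significance level of 0.05 (Statistical Analysis; sidedness is not stated, two-sided assumed). The readable text gives no sample size, power or ICC, so there is no planned figure to reproduce.

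**Assumed inputs.** Patients per hospital m = 20, 50 or 100 (23 × m = 460, 1,150 or 2,300 in total); outcome ICC 0.01, 0.02 or 0.05; factor ICC 0.1 or 0.3. An ICC is the share of variance lying between hospitals.

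**Formula.** For a patient-level factor, the variance of its estimated effect is inflated by

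DEFF = 1 + (m − 1) × ICC_outcome × ICC_factor,

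and the actual type I error of a nominal 5% test is 2 × [1 − Φ(1.96 / √DEFF)].

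**Worked cells.**

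- m = 50, ICCs 0.05 and 0.3: DEFF = 1 + 49 × 0.015 = 1.735; error 13.7%.
- m = 50, ICCs 0.02 and 0.3: DEFF = 1 + 49 × 0.006 = 1.294; error 8.5%.
- m = 100, ICCs 0.05 and 0.3: DEFF = 1 + 99 × 0.015 = 2.485; error 21.4%.

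**Full grid** (error for outcome ICC 0.01 / 0.02 / 0.05):

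| m | Factor ICC 0.1 | Factor ICC 0.3 |
|---|---|---|
| 20 | 5.2% / 5.4% / 6.1% | 5.7% / 6.3% / 8.4% |
| 50 | 5.6% / 6.1% / 7.9% | 6.7% / 8.5% / 13.7% |
| 100 | 6.2% / 7.3% / 10.9% | 8.5% / 12.1% / 21.4% |

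Four of the 18 cells exceed 10%. At factor ICC 0.05 the range is 5.1% to 7.9%. A factor unrelated to hospital has DEFF = 1 and error 5%. One balanced within hospital gives 4.4% to 4.9%. A factor constant within hospital, which the plan does not name, would give 7% to 42%.

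**Simulation of the planned methods.** No true association, 23 equal hospitals, a patient-level factor present in 40%, 4,000 runs per cell (Monte Carlo standard error at 5% is √(0.05 × 0.95 / 4,000) = 0.34 percentage points). The logistic model, for an outcome of about 30%, had no hospital term but included two other patient covariates, one unrelated to hospital and one with ICC 0.1:

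| m | Factor ICC 0.1 | Factor ICC 0.3 |
|---|---|---|
| 20 | 4.7% / 6.0% / 6.2% | 5.3% / 5.7% / 8.0% |
| 50 | 5.4% / 5.8% / 7.7% | 7.2% / 8.6% / 13.6% |
| 100 | 5.6% / 8.0% / 9.8% | 7.8% / 11.2% / 19.6% |

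With factor ICC 0 the range was 4.3% to 5.7%. At factor ICC 0.3 the other planned tests behaved alike: t test 5.5% to 20.6%, chi-square 5.6% to 19.2%, Wilcoxon on a four-level ranked outcome 5.6% to 19.3%.

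**Both must vary.** In a separate simulation of the chi-square test (m = 50 and 100, 2,000 runs per setting), error was 5.0% to 5.4% when only the factor or only the outcome varied by hospital. With factor ICC 0.20 and outcome ICC 0.05 it was 11.1% at m = 50 and 14.6% at m = 100.

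**Methods that account for hospital.** Factor ICC 0.3, nine cells, 4,000 runs each:

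- Fixed hospital effect: 4.6% to 5.2%.
- Cochran-Mantel-Haenszel (CMH): 4.4% to 5.6%.
- van Elteren: 4.7% to 5.6%.
- Logistic with hospital indicators: 4.7% to 6.3%.

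Same factor ICC, outcome ICC 0.01 and 0.05, 1,000 to 2,000 runs:

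- Logistic conditional on hospital: 4.3% to 5.0%.
- Random-intercept logistic: 3.8% to 5.6%.
- Linear random intercept, normal reference: 4.7% to 6.4%.

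**The case against.** The strongest reply is that the harm is conditional and its size wholly assumed. The documents fix only 23 hospitals and the 0.05 level. Fourteen of the 18 cells in the grid are at or below 10%, error at 20 patients per hospital never exceeds 8.4%, and nothing in the text shows that this study sits in a bad cell. That stands, and it limits the weight of the point.

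Other replies stand in part:

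- The logistic covariates are not listed, so a hospital term is not excluded, and hospital handling may be described in the design text that cannot be read. If so, the sponsor need only point to it. The argument is firmer for the t, rank sum and chi-square tests, which are named without any stratification.
- Aim one is largely descriptive, and screening is less demanding than a confirmatory test. Descriptive summaries are indeed little affected, but a screen run at 0.05 should still have an error rate near 5%.
- Confounding of medication against surgery is an inference and was not quantified. It supports the choice of method, not the size of the problem.
- The hospital-level figure of up to 42% concerns a factor the plan does not name and carries no weight here.
- The simulations used equal-sized hospitals.

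None of this shows that the planned tests account for hospital or that the replacements fail.

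**Conclusion.** The concern holds. Applied as written, the planned tests and model ignore the grouping of patients by hospital. Their p-values can be too small when, and only when, factor and outcome both vary by hospital. Under the assumed 20 to 100 patients per hospital and outcome ICC 0.01 to 0.05, actual error at the nominal 5% level runs from near 5% to about 11% at factor ICC 0.1, and from about 6% to 21% at factor ICC 0.3. Where this study falls cannot be determined from the readable text. This should be corrected, but it does not undermine the study's design or its descriptive aim. Confidence in the size is moderate because every input except the number of hospitals and the significance level is assumed.

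**What to change.** State in the Statistical Analysis section how hospital is handled. For patient-level factors, including any comparison of medication with surgery:

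- **Quantitative outcomes:** linear model with a fixed hospital effect or random hospital intercept.
- **Binary outcomes, including the risk-factor model:** CMH stratified by hospital, or logistic regression conditional on hospital or with a random hospital intercept.
- **Ranked outcomes:** van Elteren test stratified by hospital.

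Where hospital may confound, as for treatment, prefer the fixed, stratified or conditional form. These forms cannot estimate a factor that is constant within hospital. If such a factor is tested, use a random hospital intercept, or GEE clustered on hospital with a small-sample correction, since there are only 23 clusters. The corrected GEE was not simulated here.

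The cost is SAP wording and slightly more analysis work, assuming each patient's source hospital is recorded. P-values will be larger for factors that vary by hospital. Hospitals where all patients share one factor level or one outcome contribute nothing to a stratified or conditional analysis.

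### Does the acute-conditions exclusion leave 23 hospitals counting comorbidities in differently selected men?

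*Combined protocol and SAP*

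**What the plan says.** Exclusion Criteria, item 6 removes men with "The presence of acute conditions, such as, urinary tract infection, fever, heart failure etc". The readable text does not define acute and sets no time window or severity threshold.

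Three other places bear on the point:

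- Inclusion Criteria, item 4: "Clinical data comes from 23 selected hospitals spread across China". The line is therefore applied by many screeners.
- Aims: Aim one is "To investigate the symptom features and comorbidities among male lower urinary tract symptoms patients in China", and Aim two is "To determine the progression of lower urinary tract symptoms and comorbidities after medication or surgical treatment during prospective follow-ups". Comorbidity is an object of both.
- Statistical Analysis: "Categorical and ranked data will be presented using frequency and proportion". The section mentions no adjustment for, or stratification by, hospital.

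The flow diagram is not shown, and the headings Overall design, Stage I and Stage II carry no text in the copy reviewed. Operational definitions may stand there.

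**The concern.** Heart failure can be acute or chronic, and in item 6 it has no qualifier of its own. A screener who looks only at the named conditions might refuse a man with stable, long-standing heart failure, while a screener elsewhere enrols him. A similar doubt could arise over earlier urinary infection, and the open end of the list invites local additions.

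If hospitals divided in this way, item 6 would remove, at some sites only, men who carry something the study sets out to describe. The planned summary would pool the two kinds of site, and the resulting proportion would match neither reading. A man refused at entry leaves no data, so pooled analysis could not recover him. Aim two would start from the same cohort. Chronic conditions that item 6 neither names nor reaches through its open end would be unaffected.

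**Working it through.** **Step 1: what the wording settles.** The plan states no sample size, comorbidity rate or precision target, so there is no figure to reproduce and the main check is textual.

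- In item 6 the object of the exclusion is acute conditions, and they must be present. The three named conditions follow as examples, so the qualifier governs each of them.
- Item 1 of the same list uses the word chronic when it means a chronic condition (prostatitis).
- Item 4 refers to the past explicitly: "Known urinary tract, prostate or pelvic surgical history". Item 6 uses neither device.

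On a plain reading, a resolved past infection is not an exclusion, and stable chronic heart failure is not an acute condition. To exclude either, a hospital would have to disregard the word acute. This is a reading of the text, not a view on which eligibility rule is clinically right. What the text leaves open is narrower: recently decompensated heart failure, recent or recurrent infection, and whatever the open end covers.

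**Step 2: size if hospitals did divide.** Apart from the 23 hospitals, every input is an assumption: true prevalence p, number k of hospitals that exclude every case, and m men per hospital.

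With equal enrolment per hospital, the expected pooled proportion is p × (23 − k)/23. For p = 5%:

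- k = 0: 5.0%
- k = 3: 5% × 20/23 = 4.3%
- k = 6: 5% × 17/23 = 3.7%
- k = 12: 5% × 11/23 = 2.4%

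If hospitals instead screen equal numbers and the excluded men are not replaced, then with s = k/23 the proportion is p(1 − s)/(1 − ps):

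| Assumed p | k = 6 | k = 12 |
|---|---|---|
| 2% | 1.49% | 0.97% |
| 5% | 3.74% | 2.46% |
| 10% | 7.59% | 5.05% |

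The choice of denominator hardly matters.

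**Step 3: effect on a confidence interval.** Take cases as Binomial((23 − k)m, p), N = 23m, and a Wilson 95% interval on cases/N. The probability that the interval contains p is:

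| p | m (N) | k = 0 | k = 3 | k = 6 | k = 12 |
|---|---|---|---|---|---|
| 5% | 50 (1150) | 94.2% | 82.5% | 42.8% | 0.2% |
| 5% | 20 (460) | 95.9% | 93.5% | 80.6% | 21.4% |
| 2% | 50 (1150) | 95.6% | 93.1% | 80.1% | 21.7% |
| 2% | 20 (460) | 95.7% | 95.1% | 90.8% | 64.3% |

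With 3 discordant hospitals, three of the four settings keep coverage between 93.1% and 95.1%. Coverage below 50% needs 12 discordant hospitals, or 6 combined with 5% prevalence and 1150 men. The model is also all-or-nothing: a discordant hospital refuses every case. Nothing in the documents supports a value of k, and Step 1 points to k near 0. Finally, the Statistical Analysis section plans frequencies and proportions without mentioning confidence intervals, so coverage illustrates scale and is not a property of any stated analysis.

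**The case for a change.** The best case for a change is that clarification is cheap and a split reading would be costly. One reworded line sent to all hospitals, with exclusions counted by reason and site, would remove the doubt about a variable named in both aims. Acute has no definition, and heart failure is the one listed condition that a busy screener could easily take as a chronic diagnosis.

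Part of this stands. Acute is undefined, there is no time window and the list is open, so hospitals could differ on borderline cases. The arithmetic is also correct under its assumptions.

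The rest does not carry the argument. The harm needs a sizeable group of hospitals to read past a qualifier printed in the criterion, and the documents do not show that any did. They also do not say that heart failure is among the comorbidities recorded; its only mention in the readable text is item 6 itself. Counting exclusions by reason, or asking each hospital how it read the line, would only report on or repair a division that has not been shown. Conditions excluded outright at entry, such as "Existence of anatomical abnormalities of the urinary tract", have zero baseline frequency by design. How to report later cases of these is a separate matter and does not follow from any ambiguity in item 6.

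**Conclusion.** No change to the plan follows. Item 6, followed as written, excludes men with a current acute condition and gives a coherent population in which to describe comorbidity. The concern about past infection has almost no support in the text. The concern about heart failure reduces to a missing definition of acute, which sites ordinarily fill sensibly and which may already be covered in the parts of the design not shown.

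The possible distortion, from an assumed 5% down to 3.7% with 6 discordant hospitals or 2.4% with 12, depends on assumed prevalence, assumed misreading and equal enrolment. If all hospitals read the line alike, there is none. The sponsor may choose to state how borderline cases are handled, but that is optional precision. The conclusion would change only on evidence that a substantial number of hospitals refused men with stable heart failure and that heart failure is a recorded comorbidity.

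### Aim two is about change in men followed over time, but every listed test is unpaired; used on within-man change they lose power

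*Combined protocol and SAP*

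**What the plan says.** Under Aims, Aim two reads: "To determine the progression of lower urinary tract symptoms and comorbidities after medication or surgical treatment during prospective follow-ups". It does not say whether progression means change within each man, a comparison between treatment groups, or both.

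The Statistical Analysis section assigns tests by type of data, not by aim or comparison:

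- Quantitative data: "Normal distributed and equal variance quantitative data will be analyzed using independent sample t test, otherwise using a Wilcoxon rank sum test".
- Ranked data: "Ranked data will be analyzed by Wilcoxon rank sum test".
- Categorical data: "Categorical data will be assessed by Chi-square test and Fisher's exact test".
- Modelling: "Multivariate analysis logistic regression will be used to screen risk factors in the binary variables".

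No paired t test, signed-rank test, McNemar test, mixed model or GEE appears. The paragraph reads as continuous prose with no visible gap. The significance level is 0.05, with sidedness not stated. The figure under "Study design flow diagram" is not available, and the Stage I and Stage II headings carry no text in the available copy, so the visit schedule and intended comparisons cannot be checked.

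**The concern.** Each of the listed two-sample tests assumes that the two sets of values come from different people. Baseline and follow-up values from one man are usually positively correlated. The variance of their mean difference is then smaller than an unpaired test assumes.

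An analyst who applied the data-type rules to a baseline-to-follow-up comparison would therefore use too large a standard error. The test would be conservative and any confidence interval too wide. Real worsening or improvement could be reported as not significant, under one of the study's two aims. Positive correlation would not produce false claims of progression.

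**Working it through.** The plan states no sample size, power, SD, effect size or correlation, so it has no figure to reproduce. Every correlation, sample size, SD ratio and prevalence below is an assumption. Two-sided α = 0.05 is also assumed.

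**Scores, equal SDs.** Measure n men twice, with common SD σ and correlation ρ.

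- True variance of the mean difference: 2σ²(1−ρ)/n.
- Variance the unpaired test uses: 2σ²/n.
- SE ratio: k = 1/√(1−ρ).
- Actual type I error of the unpaired test: 2(1−Φ(1.96k)). Coverage of a nominal 95% interval is 1 minus this.
- Unpaired power when the paired test has power P: Φ(1.96 + z_P − 1.96k).

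Example at ρ = 0.5 and P = 80%: k = 1/√0.5 = 1.414, so 1.96k = 2.772 and Φ(1.960 + 0.842 − 2.772) = Φ(0.030) = 51.2%.

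| | ρ = 0 | 0.3 | 0.5 | 0.7 |
|---|---|---|---|---|
| SE ratio k | 1.00 | 1.20 | 1.41 | 1.83 |
| Actual type I error | 5.0% | 1.9% | 0.56% | 0.03% |
| Coverage of nominal 95% interval | 95.0% | 98.1% | 99.4% | 99.97% |
| Unpaired power, paired = 80% | 80% | 67.7% | 51.2% | 21.9% |
| Unpaired power, paired = 90% | 90% | 81.6% | 68.1% | 36.8% |
| Unpaired power, paired = 99% | 99% | 97.4% | 93.5% | 76.1% |

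Starting from 80%, power falls below 70% when 1.96k exceeds 1.960 + 0.842 − 0.524 = 2.277. That is k = 1.162, or ρ = 1 − 1/1.162² ≈ 0.26.

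A t-test simulation (n = 100, 20,000 runs) agrees. Unpaired power is 81 / 67 / 52 / 23% across the four correlations, against 79–80% for the paired test.

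**Numbers of men.** For a shift of 0.3 SD and 80% power, the paired test needs 2(1−ρ)((1.96 + 0.842)/0.3)² men. The unpaired test on the same paired data needs 2((1.96 + 0.842√(1−ρ))/0.3)². At ρ = 0.3 / 0.5 / 0.7 this gives 123 / 88 / 53 paired, against 158 / 146 / 131 unpaired.

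**Unequal SDs.** With follow-up SD s times baseline, k = √((1+s²)/(1+s²−2ρs)). At s = 1.25, k = 1.00 / 1.19 / 1.40 / 1.78, and 80% paired power falls to 80 / 68.1 / 52.5 / 24.9%.

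**Ranked data** (5 levels, n = 100, 4,000 runs). Rank sum power is 80 / 68 / 52 / 24%, against 79 / 78 / 75 / 72% for the signed-rank test at the same shifts.

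**Comorbidity status** (400 men, 30% falling to 23%, 40,000 draws). At within-man correlation φ = 0 / 0.2 / 0.4 / 0.6, McNemar's test has 61 / 71 / 83 / 95% power and chi-square 61 / 63 / 65 / 68%. Chi-square type I error at 30% prevalence is 5.0 / 2.9 / 1.2 / 0.2%.

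**Valid use of the listed test.** An independent t test on one change score per man, comparing two groups of 100 (20,000 runs), has type I error of 5.1 / 4.8 / 4.7% at ρ = 0.3 / 0.5 / 0.7. That use is sound.

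**The case against.** The strongest reply is that the plan never says an unpaired test will be applied to paired values. Aim two can be read as comparing medication with surgery. The listed tests are valid for that with one value or change score per man, and logistic regression is valid with one binary outcome per man. Descriptive summaries may also be all that is intended. The missing figure might settle the matter. This stands, and it is why the point is conditional. It does not supply a valid listed test of whether the men themselves changed, and the plan does not mention change scores.

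The second reply concerns size. Suppose 13 men at each of the 23 hospitals, 299 in all, and a shift of 0.3 SD. Unpaired power is then 97.9 / 99.2 / 99.9% at ρ = 0.3 / 0.5 / 0.7, against 99.2 / 99.9 / about 100% paired, a loss of at most 1.3 points. This also stands: in a large cohort the power loss may be slight. The excess SE does not shrink with n, though the plan does not mention confidence intervals.

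Two smaller points are fair. The unequal-SD check uses the t-test formula, whereas the plan would send such data to the rank sum test, so it supports the direction only. And the conservative direction needs positive correlation: at ρ = −0.2 the unpaired test has type I error of 7.4%. Negative correlation is not what one expects of repeated scores in one man, and the paired test is valid either way.

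**Conclusion.** The concern holds, conditionally. The Statistical Analysis section offers only unpaired tests, and the most direct reading of Aim two calls for comparison within the same men. If that comparison is run as written, the standard error is wrong: 1.20 to 1.83 times too large for correlations of 0.3 to 0.7 with equal SDs. The loss ranges from none at zero correlation, or about a point in a large cohort, to a fall from 80% to 22% at ρ = 0.7 in a study sized for the paired test. The actual loss cannot be computed from the documents. Confidence is medium, because the plan does not state that a within-man test will be run. It should be fixed before analysis, since the remedy costs almost nothing.

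**What to change.** Add a sentence to the Statistical Analysis section: any baseline-to-follow-up comparison within the same men will use the paired t test or Wilcoxon signed-rank test for scores, the signed-rank test for ranked data, and McNemar's test for comorbidity status. Only if more than two visits are analysed together, specify a mixed model or GEE that accounts for repeated measures. Keep the independent-sample tests for between-group comparisons with one record per man, including change scores, and keep logistic regression for one binary outcome per man. If no within-man test is intended, say so.

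The cost is one sentence and slightly more analysis work with standard SAS procedures (TTEST with PAIRED, UNIVARIATE, FREQ with AGREE). No new data or patients are needed. Paired tests use only men measured at both times, so report the number of pairs; the change does not by itself deal with men lost to follow-up.
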